10.6 Required Routine Reporting

10.61 Baseline and Adverse Events Evaluations

Pretreatment symptoms/conditions to be graded at baseline and adverse events to be graded at each evaluation.

Grading is per CTCAE v5.0 **unless** alternate grading is indicated in the table below:

CTCAE System/Organ/Class (SOC)	Adverse event/Symptoms	Baseline	End of C1/C2 only	Each evaluation
Blood and lymphatic disorders	Anemia	X	X	
General disorders and administration site conditions	Fatigue	X		X
Investigations	Alanine aminotransferase increased	X	X	
	Aspartate aminotransferase increased	X	X	
	Blood bilirubin increased	X	X	
	White blood cell decreased	X	X	
Musculoskeletal and connective tissue disorders	Arthralgia	X		X
Vascular disorders	Hot flashes	X		X

10.62 All other AEs

Submit via appropriate MCCC Case Report Forms (i.e., paper or electronic, as applicable) the following AEs experienced by a patient and not specified in Section 10.6:

10.621 Grade 2 AEs deemed *possibly, probably, or definitely* related to the study treatment or procedure.

10.622 Grade 3 and 4 AEs regardless of attribution to the study treatment or procedure.

10.623 Grade 5 AEs (Deaths)

10.6231 Any death within 30 days of the patient's last study treatment or procedure regardless of attribution to the study treatment or procedure.

10.6232 Any death more than 30 days after the patient's last study treatment or procedure that is felt to be at least possibly treatment related must also be submitted as a Grade 5 AE, with a CTCAE type and attribution assigned.

10.7 Late Occurring Adverse Events

Refer to the instructions in the Forms Packet (or electronic data entry screens, as applicable) regarding the submission of late occurring AEs following completion of the Active Monitoring Phase (i.e., compliance with Test Schedule in Section 4.0).

11.0 Treatment Evaluation/Measurement of Effect

Plasma concentration levels of E1 and E2 will be obtained prior to start of protocol therapy, after 8-10 weeks of anastrozole 1 mg daily (Cycle 1), after 8-10 weeks of anastrozole 10 mg daily (Cycle 2), and after 8-10 weeks of letrozole 2.5 mg daily (Cycle 3).

12.0 Descriptive Factors: None**13.0 Treatment/Follow-up Decision at Evaluation of Patient****13.1 Blood specimens**

- 13.11 Patients for whom the baseline blood sample (prior to treatment on this study) is NOT obtained and submitted, will go off study and be replaced.
- 13.12 Patients for whom the blood sample prior to ANA10 is NOT obtained will go off study and be replaced.

13.2 Anastrozole 1 mg daily for 8-10 weeks (ANA1):

- 13.21 Patients who are able to tolerate anastrozole treatment have no signs of disease recurrence may continue treatment with anastrozole for a maximum of 10 weeks.
- 13.22 Patients who are not able to tolerate anastrozole treatment or develop disease recurrence will discontinue protocol treatment and will go off study where further treatment is at the discretion of her medical team.
- 13.23 Patients who register but then refuse to begin anastrozole treatment will go off study where further treatment is at the discretion of her medical team. Baseline and on study case report forms are to be submitted. On-study material and the End of Active Treatment/Cancel Notification Form must be submitted. No further data submission is necessary.

13.3 At completion of 8-10 weeks of anastrozole 1 mg daily for 8-10 weeks

- 13.31 Patients who have completed a minimum of 8 weeks and maximum of 10 weeks of anastrozole 1 mg daily and whose plasma concentrations of E1 and E2 meet one of the following criteria:

- (a) $E1 > 1.3 \text{ pg/ml}$ and $E2 \leq 0.5 \text{ pg/ml}$
- (b) $E1 \leq 1.3 \text{ pg/ml}$ and $E2 > 0.5 \text{ pg/ml}$
- (c) $E1 \leq 1.3 \text{ pg/ml}$ and $E2 \leq 0.5 \text{ pg/ml}$

will go off study where further treatment is at the discretion of her medical team.

- 13.32 Patients who have completed a minimum of 8 weeks and maximum of 10 weeks of anastrozole 1 mg daily and whose plasma concentrations of E1 and E2 are such that:

$E1 \geq 1.3 \text{ pg/ml}$ and $E2 \geq 0.5 \text{ pg/ml}$

may re-register and begin treatment with anastrozole 10 mg daily for 8-10 weeks. Patients who choose not to re-register will go off study where further treatment is at the discretion of her medical team.

13.4 Anastrozole 10 mg daily for 8-10 weeks (ANA10):

- 13.41 Patients who are able to tolerate anastrozole treatment and have no signs of disease recurrence may continue treatment with anastrozole at 10 mg daily dose for a maximum of 10 weeks.
- 13.42 Patients who are not able to tolerate anastrozole treatment or develop disease recurrence will discontinue protocol treatment. A blood specimen is to be collected for E1 and E2 determination and then the patient will go off study where further treatment is at the discretion of her medical team.
- 13.43 Patients who re-register but then refuse to begin anastrozole treatment will go off study where further treatment is at the discretion of her medical team.

13.5 At completion of 8-10 weeks of anastrozole 10 mg daily for 8-10 weeks

Patients who have completed a minimum of 8 weeks and maximum of 10 weeks of anastrozole 10 mg daily and have a blood draw for E1 and E2 determinations may begin treatment with letrozole 2.5 mg daily for 8-10 weeks.

If the patient chooses not to begin treatment with letrozole, a blood specimen is to be collected for E1 and E2 determination. The patient will then go off study where further treatment is at the discretion of her medical team.

13.6 Letrozole 2.5 mg daily for 8-10 weeks

- 13.61 Patients who are able to tolerate letrozole treatment and have no signs of disease recurrence may continue treatment with letrozole 2.5 mg daily dose for a maximum of 10 weeks. After the completion of a minimum of 8 weeks and maximum of 10 weeks of letrozole, a blood specimen is to be collected for E1 and E2 determination. The patient will then go off study where further treatment is at the discretion of her medical team.
- 13.62 Patients who are not able to tolerate letrozole treatment or develop disease recurrence will discontinue protocol treatment. A blood specimen is to be collected for E1 and E2 determination and then the patient will go off study where further treatment is at the discretion of her medical team.

13.7 Ineligible

A patient is deemed *ineligible* if after registration, it is determined that at the time of registration, the patient did not satisfy each and every eligibility criteria for study entry. The patient will go off study where further treatment is at the discretion of her medical team. On study and end of treatment case reports are to be submitted.

13.8 Cancel

A patient is deemed a *cancel* if he/she is removed from the study for any reason before any study treatment is given. On-study material and the End of Active Treatment/Cancel Notification Form must be submitted. No further data submission is necessary.

14.0 Body Fluid Biospecimens

14.1 Summary Table of Research Blood and Body Fluid Specimens to be Collected for this Protocol

Research (Section for more information)	Specimen Purpose (check all that apply)	Mandatory or Optional	Blood or Body Fluid being Collected	Type of Collection Tube (color of tube top)	Volume to collect per tube (# of tubes to be collected)	Baseline Prior to C1D1	End of Cycle 1	End of Cycle 2	End of Cycle 3	Process at site? (Yes or No)	Temperature Conditions for Storage /Shipping
DNA	 Correlative  Eligibility Confirmation  Banking  Other (specify)	Mandatory	Whole Blood	EDTA (purple)	10 mL (2)	X				No	Ambient
E1 and E2 assays	 Correlative  Banking	Mandatory	Serum	Serum (red)	10 mL (1)	X	X	X	X	Yes	Frozen
Plasma for anastrozole	 Correlative  Banking	Mandatory	Plasma	NaHep (green)	10 mL (1)		X	X		Yes	Frozen
Plasma for letrozole	 Correlative  Banking	Mandatory	Plasma	NaHep (green)	10 mL (1)				X	Yes	Frozen

14.2 Collection and Processing

14.21 Blood for DNA

Draw two 10 ml EDTA tubes (for DNA extraction). No processing necessary.

Deliver unrefrigerated to:

Biospecimen Accessioning and Processing Lab (BAP) at each site.

BAP will perform DNA extraction from one tube. Extract buffy coat and plasma from 2nd tube and store at <-65°C.

AZ and FL will batch ship to BAP in Rochester, MN monthly.

14.22 Blood for E1/E2 Assays

14.221 Baseline

One 10 mL serum (red top) tube (for E1 and E2 assays). Serum will be divided into two aliquots with one aliquot to be sent directly to Mayo Clinic Immunochemical Core Laboratory.

Second aliquot will be stored for future use.

14.222 End of Cycles 1-3

NOTE: Blood needs to be drawn immediately before the next dose of anastrozole/letrozole to reflect steady state. Patients should be encouraged to take their anastrozole/letrozole in the morning each day EXCEPT the day of the blood draw when they should take their anastrozole after this sample has been drawn.

One 10 mL serum (red top) tube (for E1 and E2 assays). Serum will be divided into two aliquots with one aliquot to be sent directly to Mayo Clinic Immunochemical Core Laboratory.

Second aliquot will be stored for future use.

14.23 Blood for anastrozole and/or letrozole levels

One 10 mL sodium heparin tube for aromatase inhibitor level measurement by

Centrifuge within 1 hour of draw at 3000 rpm for 10 minutes.

Harvest plasma and store in 3 aliquots of approximately 1.5 mL in cryo-freezer tubes and frozen immediately at <-65°C (-80°C freezer).

Biospecimens Accessioning and Processing (BAP) will store frozen, and ship one 1.5mL aliquot from each sample drawn as a batch at the completion of the study.

The other two aliquots from each draw will be stored frozen for future use.

14.3 Shipping and Handling

14.31 Florida and Arizona only: Kits will be used for this study.

14.311 Kits will be supplied by the Biospecimen Accessioning and Processing Shared Resource (BAP).

14.312 The kit contains supplies and instructions for collecting, processing and shipping specimens.

14.313 Participating institutions may obtain kits by faxing the Supply Order Form to the number listed on the form. Because we are charged for all outgoing kits, a small, but sufficient, supply of the specimen collection kits should be ordered prior to patient entry. **Supply Order Forms must be filled in completely and legibly for quick processing.**

[figure not shown]
14.314 Kits will be sent via Fed Ex® Ground at no additional cost to the participating institutions. **Allow at least two weeks to receive the kits.**

14.315 Kits will not be sent via rush delivery service unless the participating institution provides their own Fed Ex® account number or alternate billing number for express mail. **Cost for rush delivery of kits will not be covered by the study.**

14.316 All specimens must be collected and shipped Monday – Thursday ONLY
For Mayo Clinic in Rochester, MN samples may be collected MON-FRI (as there is no shipping required)

14.32 Shipping Specimens

14.321 Shipping from Arizona and Florida
Samples should be spun down, aliquoted, and frozen prior to shipping to BAP at Mayo Clinic in Rochester, MN
Ship one aliquot frozen directly to Immunochemical Core Lab in Rochester, MN on day of collection.
Remaining samples should be shipped to BAP at Mayo Clinic in Rochester, MN on day of collection.

14.322 END OF STUDY ONLY: Shipping for anastrozole/letrozole levels
Indiana University will process the samples for drug level measurements.
Ship one 1.5 mL frozen samples per patient at end of study by overnight express service on dry ice to:
Indiana University School of Medicine
Division of Clinical Pharmacology

14.4 Background and Methodology

14.41 Estrone and estradiol assays

Pre- and post-AI treatment E1 and E2 levels will be measured by CLIA-approved liquid chromatography with tandem mass spectrometry (LC/MS/MS) assays in the Immunochemical Core Laboratory at Mayo Clinic. Details of the methodology have been published.^{13,22} The assay involves liquid extraction of 0.5 mL sample (plasma or serum depending on study) with methylene chloride

followed by derivatization with dansyl chloride, separation using a two-dimensional ultra-performance liquid chromatography system and analysis on an Agilent 6490 mass spectrometer using electrospray ionization on a positive mode. The combination of derivatization and two-dimensional chromatography (separation on two columns [Loading: Agilent Zorbax XDB-C18: 2.1 × 30 mm 3.5 micron; Analytical: Agilent Poroshell 120 EC-C18: 2.1 × 50 mm 2.7 micron]) afforded improved sensitivity and precision. Intra-assay CVs for E1 are 17.8%, 7.5%, and 6.1% at 0.30, 0.50, and 0.84 pg/mL, respectively. Intra-assay coefficients of variation (CV) for E2 are 11.8%, 7.3%, and 6.0% at 0.25, 0.51, and 0.85 pg/mL, respectively. Inter-assay CVs for E2 are 10.8%, 8.5%, and 6.9% at 0.29, 0.50, and 0.77 pg/mL, respectively.

14.42 Aromatase Inhibitor Assays

14.421 Quantification of drugs and metabolites

Anastrozole and letrozole and relevant metabolites will be measured in the laboratory of [name]., at Indiana University School of Medicine, using liquid chromatography-tandem mass spectrometry (LC/MS/MS) assays. All chemicals (anastrozole and letrozole) and internal standards (anastrozole and letrozole) will be purchased from Toronto Research Chemicals (North York, Ontario, Canada). LC-MS/MS grade water, methanol, acetonitrile, and formic acid were obtained from Fisher Scientific (Waltham, MA). Although relevant metabolites of anastrozole may be measured, these metabolites are pharmacologically inactive and their concentrations are much lower than the parent compounds.

14.422 Sample preparation

Plasma or serum sample aliquots (50 µL) will be spiked with 30 µL of an internal standard solution in methanol containing anastrozole (50 nM) for assay of letrozole samples and letrozole (50 nM) for assay of anastrozole samples. LC-MS/MS grade methanol (220 µL) was added to precipitate proteins followed by vortex mixing (90 seconds, 2,000 rpm), and centrifugation (20 minutes, 3,000 rpm, 4°C). The resulting supernatant (150 µL) will be transferred to clean plates for analysis via LC-MS/MS.

14.423 LC-MS/MS Method

Chromatographic separation for anastrozole, letrozole, and respective metabolites will be achieved using an Acquity BEH C18 column (1.7 µM, 2.1 x 100 mm) with a Critical Clean precolumn filter (2.1 x 0.2 µM) (Waters) heated to 35°C and a binary gradient at a flow rate of 0.4 ml/min. The gradient elution will be held at 65:35 mobile phase A (5 mM ammonium formate with 0.1% formic acid in water): mobile phase B (acetonitrile with 0.1% formic acid) for 1 minute. Then this will be increased linearly to 52% mobile phase B over 30 seconds, held at 52% for 2.5 minutes followed by increase to 100% mobile phase B over 30 seconds, and then held at 100% for 30 seconds before returning to initial conditions over 0.5 minutes. The total run time is expected to be six minutes. Samples will be analyzed (2 µL injection volume) using the QTRAP 6500+ UHPLC-MS/MS system (AB Sciex) with the turbo electrospray source operated in positive ion mode.

Anastrozole (294-225), hydroxy-anastrozole (310-241), anastrozole-N-glucuronide (470-294), anastrozole-O-glucuronide 1 (486- 310), anastrozole-O-glucuronide 2 (486+310), and letrozole (286-217) m/z transitions will be monitored in multiple reaction monitoring mode. Anastrozole-O- glucuronide 1 and 2 will be denoted based on differences in retention time.

15.0 Drug Information

15.1 Anastrozole (Arimidex®)

15.11 Background

Anastrozole is a nonsteroidal, competitive inhibitor of the aromatase enzyme system which binds to the heme group of aromatase, a cytochrome P450 enzyme that catalyzes the conversion of androgens to estrogens.

15.12 Formulation and storage

Anastrozole is commercially available as 1 mg tablets. Store at controlled room temperature 20-25°C (68-77°F) [see USP Controlled Room Temperature].

15.13 Administration

Administer orally with or without food. Refer to the treatment section for specific administration instructions.

15.14 Pharmacokinetic information

Absorption: Absorption of anastrozole is rapid and maximum plasma concentrations typically occur within 2 hours of dosing under fasted conditions. Food reduces the rate but not the overall extent of anastrozole absorption.

Distribution: Plasma concentrations approach steady-state levels at about 7 days of once daily dosing. Anastrozole is 40% bound to plasma proteins in the therapeutic range.

Metabolism: Metabolism of anastrozole occurs by N-dealkylation, hydroxylation and glucuronidation.

Excretion: Eighty-five percent of radiolabeled anastrozole was recovered in feces and urine. Hepatic metabolism accounts for approximately 85% of anastrozole elimination. Renal elimination accounts for approximately 10% of total clearance. The mean elimination half-life of anastrozole is 50 hours.

15.15 Potential drug interactions

Cytochrome P450: None

15.16 Known potential adverse events

Consult the package insert for the most current and complete information. Common adverse reactions include hot flashes, asthenia, arthritis, pain, arthralgia, pharyngitis, hypertension, depression, nausea and vomiting, rash, osteoporosis, fractures, back pain, insomnia, headache, bone pain, peripheral edema, increased cough, dyspnea and lymphedema.

15.17 Drug procurement

Anastrozole 1 mg is commercially available: Patients will be given a prescription for anastrozole to be filled at the pharmacy of their choice.

Anastrozole 10 mg: Study medication will be provided by the Mayo Clinic Breast Cancer SPORE.

15.18 Nursing guidelines

15.181 May take with food if needed for nausea. Instruct patient to report unrelieved nausea or vomiting.

- 15.182 Instruct patient that hot flashes may occur. Manage hot flashes with non-hormonal interventions (e.g. venlafaxine XR 75 mg daily).
- 15.183 Assess for changes in bowel patterns. Manage diarrhea with non-prescription drugs. Instruct patient to report unrelieved diarrhea.
- 15.184 Headache may occur. Can be managed with non-prescription analgesics. Instruct patient to report headaches that are not relieved.
- 15.185 Vaginal dryness may occur. Instruct patient in the use of lubricating agents.
- 15.186 Mild swelling may occur in the arms and legs. Instruct patient to elevate extremities when at rest to relieve the swelling.
- 15.187 While thrombophlebitis is rare, instruct patient to report any pain, redness, marked swelling in the arms and/or legs, dizziness, or shortness of breath to their health care provider immediately or seek medical attention in an emergency room.

15.2 Letrozole (Femara®)

15.21 Background

Letrozole is a nonsteroidal, competitive inhibitor of the aromatase enzyme system which binds to the heme group of aromatase, a cytochrome P450 enzyme that catalyzes the conversion of androgens to estrogens.

15.22 Formulation and storage

Letrozole is commercially available as 2.5 mg tablets. Store at 77°F (25°C); excursions permitted to 59°F to 86°F (15°C to 30°C) [see USP Controlled Room Temperature].

15.23 Administration

Administer orally with or without food.

Refer to the treatment section for specific administration instructions.

15.24 Pharmacokinetic information

Distribution: V_d : ~1.9 L/kg

Protein binding: weak

Metabolism: Hepatic via CYP3A4 and CYP2A6 into an inactive carbinol metabolite

Half-life elimination: Terminal: ~ 2 days

Excretion: Urine (90%; 6% as unchanged drug, 75% as glucuronide carbinol metabolite, 9% as unidentified metabolites)

15.25 Potential Drug Interactions

Cytochrome P450: Substrate of CY2A6 (minor), CYP3A4 (minor).

Inhibitor of CYP2A6 (strong), CYP2C19 (moderate)

15.26 Known potential adverse events:

Consult the package insert for the most current and complete information.

Common adverse events include cataracts, eye irritation, palpitations, cardiac failure, tachycardia, dysaesthesia, arterial thrombosis, memory impairment, irritability, nervousness, urticaria, increased urinary

frequency, leukopenia, stomatitis, pyrexia, vaginal discharge, appetite increase, dryness of skin and mucosa and disturbances in taste and thirst.

15.27 Drug procurement

Commercial supplies. Patients will be given a prescription for letrozole to be filled at the pharmacy of their choice.

15.28 Nursing Guidelines

15.281 Manage hot flashes with non-hormonal interventions (e.g., venlafaxine XR 75 mg daily).

15.282 Manage pain (arthralgias). Instruct patient to report unrelieved pain.

15.283 May take with food if needed for nausea. Instruct patient to report unrelieved nausea or vomiting.

15.284 Assess for changes in bowel patterns. Manage diarrhea or constipation with non-prescription drugs. Tell patients to report unrelieved diarrhea or constipation.

15.285 If patient experiences difficulty breathing or sudden onset chest pain, instruct them to seek emergency medical attention immediately.

15.286 Monitor for signs of edema, instruct patient to report any swelling in legs, feet, or hands.

16.0 Statistical Considerations and Methodology

16.1 Study Design

This goal of this study is to assess whether women with inadequate estrogen suppression after 8-10 weeks of adjuvant anastrozole 1 mg daily (ANA1) would benefit from increasing their dose of anastrozole to 10 mg daily (ANA10). Two analytic approaches will be taken to address this objective. The first approach focuses on the set of patients who are adherent to treatment schedule, that is, if at least 80% of the planned dose is taken will adequate estrogen suppression be achieved. The second approach focuses on intentions, that is, among those patients who start an 8-10 week course of anastrozole 10 mg daily what proportion will have achieved adequate estrogen suppression at treatment discontinuation. Patients who fail to provide a blood sample after discontinuing treatment will be considered not to have achieved adequate estrogen suppression.

The study was designed to assess in the adherent cohort whether the estrogen suppression rate with anastrozole 10 mg daily for 8-10 weeks (ES-ANA10) after inadequate estrogen suppression of 8-10 weeks of adjuvant anastrozole 1 mg daily is at most 25% against the alternative that it is at least 50%.

Inadequate estrogen suppression is defined as $E1 > 1.3 \text{ pg/ml}$ and $E2 > 0.5 \text{ pg/ml}$ after 8-10 weeks of treatment with an aromatase inhibitor.

Based on preliminary findings from MA27, we expect approximately 20% of women with ER+ primary breast cancer to have inadequate estrogen suppression with anastrozole 1 mg daily for 8-10 weeks. Thus, if 160 patients were enrolled then we would expect 32 of them to have IES-ANA1. There may be a few patients who refuse to switch to anastrozole 10 mg daily for 8-10 weeks followed by a blood draw for E1 and E2 testing.

Assuming at most 3 women will refuse to continue or fail to adhere to treatment, 29 patients who are adherent to treatment will be available to evaluate the primary aim.

With a sample size of 29 patients in the adherence cohort, a one-sided binomial test of proportions with a significance level of 0.05 will have a 87% chance of rejecting the null hypothesis that the estrogen suppression rate with anastrozole 10 mg daily for 8-10 weeks is at most 25% when the true estrogen suppression rate with anastrozole 10 mg daily for 8-10 weeks is at least 50%. Specifically, the null hypothesis is rejected if the number of women who are ES-ANA10 is 12 or more among these 29 patients.

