2.0 Goals**2.1 Primary Goal**

To estimate the proportion of women who have adequate estrone (E1) and estradiol (E2) suppression after 8-10 weeks of adjuvant anastrozole 10 mg once daily (ANA10) having had inadequate E1 and E2 suppression after 8-10 weeks of standard dose anastrozole 1 mg once daily (ANA1).

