3.3 Re-Registration – Inclusion Criteria

3.31 Confirmation that baseline blood sample was drawn and submitted.

3.32 Blood estrogen levels after Cycle 1anastrozole (ANA1) must meet the following criteria:
 $E1 \geq 1.3 \text{ pg/ml}$, AND
 $E2 \geq 0.5 \text{ pg/ml}$

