7.3 Cycle 1 Anastrozole (ANA1)

7.31 Basics

A research blood sample must be drawn at baseline prior to treatment or patient is unevaluable and must be replaced.

All patients will be prescribed the FDA-approved dose of anastrozole at 1mg daily (standard adjuvant dose) for the first 8-10 weeks.

At the end of the first cycle, blood will be drawn for drug levels and E1 and E2 levels.

Patients should be encouraged to take their anastrozole in the morning each day EXCEPT the day of the blood draw when they should take their anastrozole after this sample has been drawn.

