7.32 Blood draw at end of cycle

Patients will have blood drawn for estrone and estradiol concentrations and all samples for the week will be batched for processing in the Immunochemical Core Laboratory the following Monday.

Results will be reported the following day (usually Tuesday).

Patients who do not meet the following criteria will be given a recommendation for 5 years of anastrozole and go off study.

E1 \geq 1.3 pg/ml

AND

E2 \geq 0.5 pg/ml

Patients whose estrogen levels meet these criteria and are willing to continue will proceed to Cycle 2.

NOTE: Patients unwilling to continue will go off study and be replaced.

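### Section 16.1 asks whether women benefit from a higher dose, but its test only compares the ANA10 suppression rate with 25%, and some women selected on one reading will convert without any dose effect

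*Combined protocol and SAP*

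**What the plan says.** Section 2.1 gives the primary goal as an estimate: "To estimate the proportion of women who have adequate estrone (E1) and estradiol (E2) suppression" on ANA10 after inadequate suppression on ANA1. Section 16.1 opens with a different question, whether these women "would benefit from increasing their dose of anastrozole to 10 mg daily (ANA10"). It then tests whether the ANA10 suppression rate "is at most 25% against the alternative that it is at least 50" per cent, rejecting the null at 12 or more of 29 women. Section 16.2.1 adds binomial point and interval estimates of the same rate. No source is given for 25%.

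Selection uses one draw: "At the end of the first cycle, blood will be drawn for drug levels and E1 and E2 levels" (7.31). Under 3.32, "Blood estrogen levels after Cycle 1anastrozole (ANA1) must meet the following criteria": E1 >= 1.3 pg/mL and E2 >= 0.5 pg/mL. Under 7.32, "Patients whose estrogen levels meet these criteria and are willing to continue will proceed to Cycle 2". Section 14.222 sends one serum aliquot for assay and stores the other. No repeat reading on 1 mg and no group kept on 1 mg is planned.

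Sections 16.1 and 16.41 define inadequate suppression as E1 > 1.3 and E2 > 0.5.

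Section 11.0 provides for E1 and E2 levels "after 8-10 weeks of anastrozole 1 mg daily (Cycle 1), after 8-10 weeks of anastrozole 10 mg daily (Cycle 2"), but 16.5 defines percent change from pre-AI levels only.

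**The concern.** A woman enters ANA10 only if both hormones are high on a single reading. By the complement of the 16.1 definition, she succeeds if either is no longer high on a single later reading. Any variation between readings at a constant dose will move some women across a threshold, and selecting on high values makes that movement mostly downward (regression to the mean).

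A count of 12 of 29 would support a suppression rate above 25% on ANA10. Read as the opening of 16.1 invites, it would also credit the dose with conversions that a second reading on 1 mg might have shown. The within-woman contrast closest to the dose question, the concentration change from end of Cycle 1 to end of Cycle 2, is not defined although both samples are taken.

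**Working it through.** **1. The plan's own figures.** 160 x 0.20 = 32, and 32 - 3 = 29. With X ~ Binomial(29, p):
- P(X >= 12 | p = 0.25) = 0.039, the actual one-sided alpha.
- P(X >= 12 | p = 0.50) = 0.868, matching the stated 87%.
- P(X >= 11 | p = 0.25) = 0.086, so 12 is the smallest valid cut-off.

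**2. Chance of meeting the rule with no dose effect**, if c is the share of selected women who would convert at an unchanged dose, from P(X >= 12 | p = c):

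| c | 15% | 20% | 25% | 30% | 35% | 40% |
|---|---|---|---|---|---|---|
| P | 0.0005 | 0.007 | 0.039 | 0.129 | 0.295 | 0.510 |

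As a test of dose effect, the rule keeps its 5% error only if c is about 25% or less.

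**3. Inputs for c.**
- From 1.1: on anastrozole, 41.3% of E1 and 11.9% of E2 values were below LLQ; the E1-E2 Spearman correlation was 0.54.
- From 1.2: LLQs of 1.0 and 0.3 pg/mL; 85th percentiles of 1.7 and 0.7 pg/mL.
- From 14.41: E2 inter-assay CV of 8.5% at 0.50 pg/mL, represented by a CV of 8%.
- From 16.1: 20% expected to be inadequately suppressed.
- Assumed: lognormal values; total within-woman CVs of 15%, 20% and 25%; error correlation between hormones of 0 or 0.5; unrounded values.

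**4. Model.** log Y(visit) = log true level + error(visit), with the true level unchanged between visits. Select if Y1 is >= 1.3 for E1 and >= 0.5 for E2, then read Y2. Four fits were used. Fit A takes 1.7 and 0.7 as 85th percentiles (selects 23.7%). For E1, sigma = ln(1.7/1.0)/(1.036 + 0.220) = 0.42. Fit B takes them as assumed 78th and 81st anastrozole percentiles, because the quoted percentiles pool the drugs (selects 27.6%). The other two shift A and B to select 20%. Each setting used 1.5 million draws. Ranges run over the fits and error correlations.

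| Within-woman CV | No-effect conversion, at least one hormone below | P(>= 12/29) | No-effect conversion, both below | No-effect median fall, Cycle 1 to 2 |
|---|---|---|---|---|
| 8% (assay level) | 12%-17% | at most 0.001 | about 1%-2% | 1%-2% |
| 15% (assumed) | 21%-31% | 0.01-0.14 | about 2%-7% | 3%-6% |
| 20% (assumed) | 28%-40% | 0.08-0.51 | 4%-12% | 5%-11% |
| 25% (assumed) | 33%-49% | 0.23-0.85 | 6%-19% | 8%-16% |

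Under the one-hormone reading, conversion reaches 25% at a CV of 12%-18%, depending on the fit.

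**5. Cross-check.** Expressed as test-retest reliability instead (20% selected, correlation 0.54), no-effect conversion is 18%-19% at an ICC of 0.95, 25%-26% at 0.90 and 34%-37% at 0.80.

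**6. The concentration change has the same problem.** With no dose effect, 29 pairs and an order-statistic 95% interval for the median change, the interval shows a fall in at least one hormone in roughly 15%-46% of simulated trials at a CV of 20%.

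**7. Boundary values.** Take E1 = 1.3 and E2 = 0.9 at both visits. The woman meets 3.32 and 13.32 and may enter ANA10. She also meets 13.31(b) and would go off study. At end of Cycle 2 the identical reading is not inadequate under 16.1, so she counts as suppressed.

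**The case against.** The strongest reply is that this is mostly wording. Goal 2.1 is an estimation goal and the design delivers it. Section 16.1 at once turns its question into two analyses of whether suppression is achieved. Section 1.4 also says that long-term benefit of 10 mg is not yet known. All of this stands, but 1.4 limits the long-term clinical claim, not the claim that the higher dose caused the conversions.

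Second, the null is 25%, not zero. At the only error level documented, no-effect conversion is 12%-17% and the rule is conservative. If Goal 2.1 means that both hormones must be suppressed, 25% is enough at every CV examined. This stands too. A reader might infer that 25% is too low, or that the trial is likely to succeed falsely. The documents do not support that: the higher conversion rates rest on assumed CVs and on the one-hormone reading. They equally do not say that 25% was chosen to allow for such conversion.

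Third, a reader might infer that change from Cycle 1 to Cycle 2 is not analysed at all. It is: the primary endpoint is a change of status from inadequate at end of Cycle 1, and Goal 2.22 covers women whose levels stay elevated. Only a defined concentration change is missing, and 16.5's spider plots may already show individual paths.

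**Conclusion.** The point holds in a limited form. Rejecting 25% would establish a suppression rate above 25% on ANA10. It would not by itself establish benefit from raising the dose, because selection rests on one reading and nobody is measured again on 1 mg.

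Whether 25% covers conversion without a dose effect is unknown. It does at assay-level error and under the both-hormones reading. Under the one-hormone reading it may not once total within-woman CV passes about 12%-18%. The documents give assay CVs only, and for E1 no inter-assay CV and none above 0.84 pg/mL. The figures also assume lognormal values, the earlier study's LLQs and percentiles, and unrounded results.

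It would be tempting to treat a paired Cycle 1 to Cycle 2 change as settling attribution. It cannot, since it is taken in the same women selected on the same reading. Attribution would need a repeat reading on 1 mg, a null justified from test-retest data, or a concurrent comparison. Severity is low to moderate. The mismatch between >= and > is a separate inconsistency that can be checked from the text alone.

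**What to change.** (a) In 16.1, state that rejecting 25% supports a suppression rate above 25% on ANA10 (Goal 2.1) and does not by itself establish benefit from raising the dose, because women are selected on one elevated reading and none is re-measured on 1 mg. State also whether success means one hormone or both below threshold.

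(b) In 16.5, add as descriptive and supportive only: the median percent change in E1 and in E2 from end of Cycle 1 to end of Cycle 2, with individual paths and below-LLQ values set to this trial's LLQ (which understates falls). Say that selection on the Cycle 1 reading inflates this change, so an interval excluding zero is not evidence of a dose effect.

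Optionally, add a count in which the hormone that drops must fall by more than a pre-stated measurement-error margin. For E2 this could be 1.645 x sqrt(2) x 8.5% = 19.8%, about 20%. It covers assay error only, and the E1 margin needs laboratory data. At a CV of 25% it still leaves 28%-42% no-effect conversion, and for a true 20% fall in both hormones it lowers the count by 4-16 points, so it cannot replace the test.

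(c) Separately, reconcile the >= entry rule (3.32, 7.32, 13.32) with the > definition (16.1, 16.41), including the overlap of 13.31 and 13.32 at the thresholds.

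Items (a) and (b) are wording and analysis of samples already collected. The test, sample size and visits are unchanged. Item (c) is a text reconciliation.
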